4.2 Scientific Rationale for Study Design

The non-vaping group MRI will serve as a comparison against the frequent nicotine vaping group to characterize static and dynamic rsFC alterations in hippocampal networks related to frequent nicotine vaping in adolescents (Objective 1). Frequent nicotine vaping adolescents will participate in two MRI scan visit days (pre- and post- MBSR intervention) to characterize rsFC changes (Δ rsFC) in hippocampal networks following the intervention (Objective 2).

4.3 Justification for Intervention

As discussed in section 2.2, MBSR engages brain regions involved in tobacco use disorder. Sibinga and others, (2011-2018) have conducted multiple RCTs of MBSR in diverse youth populations. Across studies, her research has shown that participation in MBSR leads to improvements in psychological symptoms and health behaviors in at-risk urban youth.⁸¹⁻⁸⁴ We will use the same 9-week MBSR treatment protocol and the same MBSR trainer as previously used in these studies conducted in similar populations in the Baltimore area.

4.4 End-Of-Study Definition

A frequent nicotine vaping participant is considered to have completed the study if they have completed the baseline assessment, all 9 weeks of the MBSR intervention, the pre- and post-intervention MRI scans, and the follow-up assessments. There will be an end of intervention assessment and three follow-up assessments (once per month for three months and may be conducted virtually) after the last MRI scan. The final follow-up marks the end of the study for the participant.

A non-vaping participant is considered to have completed the study if they have completed the baseline assessment and one MRI scan.

(SoA), **Section Error! Reference source not found..**

Abbreviated Title: Mindfulness and Teen Vaping

Version Date: 07/21/2025

NIH IRB#: IRB001855

5 STUDY POPULATION

5.1 Inclusion Criteria

In order to be eligible to participate in this study, an individual must meet all of the following criteria:

Non-Vaping group:

1. For adolescents aged 17 and under, parental/guardian informed consent to participate in the study
2. English language fluency
3. Males and females; Age 13-18 enrolled in grades 9-12, or the summer after graduation.
4. No MRI contraindications
5. No evidence of current psychosis, mania, or significant suicidality
6. If on medication for depression, anxiety or ADHD, dose has been stable for 3 months
7. No DSM-5 diagnosis of moderate or severe SUD related to a psychoactive substance, including tobacco, in the past year
8. Access to necessary resources for participating in a technology-based intervention, which includes smartphone ownership for this study
9. No use of nicotine more than 5 times in their life, and none at all in the last 30 days prior to enrollment.

Vaping group:

1. For adolescents aged 17 and under, parental/guardian informed consent to participate in the study
2. English language fluency
3. Males and females; Age 13-18 enrolled in grades 9-12, or the summer after graduation.
4. No MRI contraindications
5. No evidence of current psychosis, mania, or significant suicidality
6. If on medication for depression, anxiety or ADHD, dose has been stable for 3 months
7. No DSM-5 diagnosis of moderate or severe SUD related to another psychoactive substance (other than tobacco) in the past year
8. Vape a nicotine containing product at least 10 days in the past 30 days
9. Access to necessary resources for participating in a technology-based intervention, which includes smartphone ownership for this study

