5.2 Exclusion Criteria

An individual who meets any of the following criteria will be excluded from participation in this study based on self and or parent-report unless otherwise noted:

Vaping or Non-Vaping Group:

1. Chronic medical conditions associated with cerebral blood flow abnormalities per PI/MAI determination after review of the medical history.
2. Neurological conditions that may interfere with MRI data quality per PI/MAI determination after review of the medical history.

Abbreviated Title: Mindfulness and Teen Vaping

Version Date: 07/21/2025

NIH IRB#: IRB001855

3. Neurodevelopmental disorders that are likely to significantly affect data in the judgment of the MAI/PI
4. Non-penetrating traumatic brain injury with loss of consciousness > 30 minutes or significant sequelae persisting longer than 2 weeks or any penetrating traumatic brain injury.
5. Changing dose of psychotropic medication in past 3 months
6. Current regular meditation or yoga practice averaging >10 min/day for >2 days per week
7. Pregnancy, self-report upon protocol entry, but by urine test prior to MRI scan.

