8.1.2 Screening activities performed after a consent for screening has been signed

At the first visit, after consent/assent is obtained, the following measures will be gathered to further assess eligibility for the study:

Diagnostic Assessment (~1.5 hours)

- a. Clinical history – clinician review
- b. Mini International Neuropsychiatric Interview for Children and Adolescents-DSM-5.0 version (MINI-KID-5) or SCID-RV
- c. MRI Safety Assessment
- a. Substance Use History
 - General Substance Use History Questionnaire (with tobacco & e-cigarette smoking, alcohol, and cannabis questions included)
 - Cannabis Use Disorder Test (CUDIT, 8 items, ~1-2 min)

8.2 Study Evaluations & Procedures after eligibility has been determined.

Administration of questionnaires, interviews, or other instruments (Table 1).

Abbreviated Title: Mindfulness and Teen Vaping

Version Date: 07/21/2025

NIH IRB#: IRB001855

The consent, screening activities listed in 8.1.2, and the baseline assessments listed below may be completed in the same visit virtually or in-person, and all or some of these procedures may also be completed in the same visit as the first scan session. Some questionnaires may be completed virtually in between the consent appointment and Scan Day 1.

Orientation and Initial Baseline Assessments (Visit(s) 1, may be conducted virtually) (~35-55 min):

Demographics and Puberty (~2-5min)

- a. Demographics questionnaire
- b. Pubertal Development Scale

Substance Use Measures

- a. General Substance Use (all participants)
 - Timeline Follow-back (TLFB)
 - Past 28-days tobacco vaping (vaping days and vapes or puffs/day), tobacco smoking, cannabis, alcohol, other drugs if relevant. 7-day TLFB for later visits for vaping teens.
 - Craving Questionnaire (~1-5 min)
- b. E-Cigarette Measures (Vapers only)
 - E-cigarette Dependence Scale (EDS, 4 items, 1 min)
 - Nicotine Social Influence Questionnaire (NSIQ, 1 min)
 - Social influence - peer and family e-cigarette use and approval
 - Modified E-Cigarette Fagerstrom Test for Nicotine Dependence (FTND, 8 items, 1-2 min)

Psychological Measures

- Sensitivity to Reward and Sensitivity to Punishment Questionnaire (SRSPQ, 48 items, 5 min)
- Patient Health Questionnaire-9 (PHQ-9, 9 items, 2 min)
 - Assesses degree of depression severity
- General Anxiety Disorder-7 (GAD-7, 7 items, 2 min)
- Difficulty in Emotion Regulation Scale (36 items, 4 min)
- 5-trial Adjusting Delay Discounting Task (bench, 2 min)

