8.2.1 Biospecimen Evaluations

The following biospecimen tests will be collected at scan 1 (Visit 1), scan 2 (Visit 11), and follow-up visits (12-15) to measure nicotine, THC, alcohol, and other drug use.

- Urine Cotinine Test, Urine Drug Test (UDT)
- Breath CO and ALC test

Urine samples acquired for measurements of pregnancy and drug usage at each visit will be destroyed once valid assays have been obtained.

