9.3 Populations for Analyses

- Modified Intention-to-Treat Analysis Dataset: All frequent nicotine vaping participants approved to participate in the MBSR intervention who complete the first scan day will be included in the comparison of vaping to non-vaping teens. Non-vaping teens who complete the scan will be included in this analysis.
Frequent nicotine vaping participants who completed the study intervention (regardless of number of sessions actually attended) and complete both MRI scans will be included in the pre-post imaging comparison in the vaping group. If they also complete at least one follow-up visit, they will be included in the assessment of effect of MBSR on vaping and related outcome measures.

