9.4.5 Baseline Descriptive Statistics

Tobacco vaping and other drug use measures: Tobacco vaping/e-cigarette use (vaping days, vapes/vaping day) and other drug use in the past 28 days will be collected via TLFB at baseline and post-MBSR MRI follow-up visit. Additional information on time to first vape, nicotine concentration used, vape device used, use of flavors, social influence will be collected along with validated instruments measuring e-cigarette dependence (EDS).

Biochemical measures of drug use: Semi-quantitative urine cotinine testing and carbon monoxide (CO) monitoring will be used to verify self-reported post-MBSR abstinence. Urine drug testing, and breath alcohol level will be collected.

Other self-report assessments: Self-report measures of mood, anxiety, coping, emotion regulation, cognitive function and mindfulness found to show changes following MT in prior studies will be collected and used in theory-driven exploratory analyses.

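### Control status for Primary Endpoint 1 has no biochemical check, although urine cotinine is taken before scan 1

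*Combined protocol and SAP*

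**What the plan says.** All references are to the combined protocol and SAP.

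- **Group definitions (5.1).** A control must satisfy "No use of nicotine more than 5 times in their life, and none at all in the last 30 days prior to enrollment". A vaping participant must "Vape a nicotine containing product at least 10 days in the past 30 days". Neither criterion names a test.
- **Exclusions (5.2).** A person meeting one "will be excluded from participation in this study based on self and or parent-report unless otherwise noted". The only criterion there tied to a urine test is "Pregnancy, self-report upon protocol entry, but by urine test prior to MRI scan".
- **Eligibility after consent (8.1.2).** Here "the following measures will be gathered to further assess eligibility for the study": clinician-reviewed history, a structured diagnostic interview, MRI safety, and substance-use and cannabis questionnaires. Cotinine is not listed.
- **Scan day (8.2).** A nursing evaluation that includes urine cotinine and breath CO comes before the MRI. It is not limited to vapers, and the biospecimen row of Table 1 has no such limit either. The only action rule, here and in 5.6, concerns a positive urine drug test together with evidence of intoxication on clinical assessment.
- **Purpose of the samples (8.2.1).** "The following biospecimen tests will be collected at scan 1 (Visit 1), scan 2 (Visit 11), and follow-up visits (12-15) to measure nicotine" and other substances.
- **Use of cotinine in the analysis.** In 9.4.3 it is paired with the timeline follow-back for change in vaping frequency. In 9.4.5 cotinine and CO "will be used to verify self-reported post-MBSR abstinence".
- **Analysis set and test.** Section 9.3: "Non-vaping teens who complete the scan will be included in this analysis". Section 9.4.2 compares the groups with independent t-tests and lists no cotinine term.

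**The concern.** Primary Endpoint 1 contrasts nicotine-exposed with unexposed adolescents, so it depends on the controls being unexposed. The plan collects an objective marker of recent exposure from controls before the scan, but gives that result no role in eligibility, group assignment or the analysis set. A teen who denies use and tests positive can therefore be scanned and analysed as unexposed.

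Any such participants would pull the control mean towards the vaping mean. A null or weak result could then not be separated from misclassification. If the team instead dropped cotinine-positive controls case by case, without a rule written beforehand, the choice of controls would be open to question.

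**Working it through.** **Step 1. The plan's own sample-size figures.** Section 9.2 cites a task-fMRI simulation with an inter-participant SD of 0.5%, an intra-participant SD of 0.75% and about 100 time points. It gives 11 participants (0.5% signal, p<0.05), 21 (0.5%, p<0.002) and 11 (0.75%, p<0.002) for power 0.8.

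SD = √(0.5² + 0.75²/100) = 0.506. A two-sided one-sample t-test then needs 11, 21 and 12, which reproduces the stated figures to within one participant.

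Put into a two-group normal formula for a 0.5% difference, the same inputs give 17 (p<0.05) and 32 (p<0.002) per group. These inputs concern task signal. The plan states no effect size for a group difference in connectivity, so the 40 per group comes with no stated margin against dilution.

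**Step 2. Attenuation.** Let m be the share of controls who recently used nicotine, and k their mean shift as a fraction of the vapers' shift. The documents give neither, so both are assumptions.

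Observed difference / true difference = 1 − m·k

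| m (of 40 controls) | k = 1 | k = 0.5 |
|---|---|---|
| 5% (2) | 0.95 | 0.975 |
| 10% (4) | 0.90 | 0.95 |
| 20% (8) | 0.80 | 0.90 |

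For k = 1 the sample inflation needed for equal precision relative to effect is 1/(1−m)²: 1/0.95² = 1.11, 1/0.90² = 1.23, 1/0.80² = 1.56.

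**Step 3. Power at 40 versus 40.** Take the standardised difference d that gives exactly 80% power without misclassification: d = 0.634 at two-sided α = 0.05 and d = 0.907 at α = 0.002, the threshold 9.2 links to cluster correction. With k = 1 the observed difference is d(1−m) and the control variance is 1 + m(1−m)d².

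| m | Power, α = 0.05 | Power, α = 0.002 | Per group to regain 80% |
|---|---|---|---|
| 2.5% (1) | 77.8% | 76.6% | 43 |
| 5% (2) | 75.5% | 72.9% | 45 |
| 10% (4) | 70.5% | 65.0% | 51 |
| 20% (8) | 59.7% | 48.3% | 64–65 |

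**Step 4. Effect of a cotinine rule, if it removes all such controls.** With replacement back to 40, power returns to 80%. With removal and no replacement at m = 5%, 10% and 20%, power is 78.9%, 77.8% and 75.1% (α = 0.05), or 78.5%, 76.7% and 72.7% (α = 0.002). Under k = 1, removal without replacement already recovers most of the loss.

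**The case against.** The strongest reply is that 5.1 sets a fact about use, not an answer to a question. A teen shown to have used nicotine in the last 30 days fails the criterion, and 7.2 lists screen failure among the reasons for which an investigator may discontinue a participant. The report-based wording in 5.2 governs exclusions only. This stands in part: the documents do not oblige a site to keep a cotinine-positive control. But removal is discretionary, cotinine is not named as a trigger, and 9.3 states its inclusion rule without reference to it.

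Several stronger readings are tempting and are not supported:

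- *Group status rests on bare questionnaire answers.* It does not. There is a clinician-reviewed history, a structured interview and a 28-day timeline follow-back. All still depend on report.
- *Cotinine serves only to verify abstinence.* Section 9.4.3 also uses it for change in vaping frequency, which implies a baseline value in vapers. That still leaves control status unchecked.
- *Minors answer in front of a parent.* Section 5.6 requires a parent for consent only and makes staying optional; 10.3 asks for as private a setting as possible.
- *The vaping group contains unexposed teens.* The criterion already requires a nicotine product, and 9.4.5 records concentration and device. Dual users are admitted, so a positive cotinine would not show that the vape was the source.

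The limits of the test also stand. It is described as semi-quantitative with no cut-off given. It reflects recent use, may miss intermittent users, and cannot check the lifetime limit of five uses. Breath CO bears on smoked rather than vaped product. In a self-described small pilot, these points argue for a modest change, not against one.

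**Conclusion.** The gap is real. Control status for Primary Endpoint 1 is not checked biochemically, although the sample is taken before the scan, and no rule links its result to eligibility or to the 9.3 analysis set.

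A reader might infer that the endpoint is in fact diluted. The documents do not support that, because they give no misclassification rate. The conclusion is conditional: the difference would shrink roughly in proportion to the share of recent users among controls. One such control in 40 would cost about 2 to 3 power points. At 5% to 10% the cost is about 5 to 10 points at α = 0.05 and 7 to 15 at α = 0.002. These figures assume 80% power to begin with and hidden users who resemble regular vapers, so they overstate the loss for lighter users.

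The change is worth making because it is cheap and makes a null result easier to interpret, not because harm has been shown.

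**What to change.** 1. **5.1 and 9.3.** State in advance that a non-vaping participant enters the Primary Endpoint 1 control set only with scan-1 urine cotinine below the assay's cut-off, and write that cut-off into the protocol. Allow one pre-specified repeat where passive exposure is credible. Replace excluded controls within the ceiling of 60 enrolled per group in 4.1.
2. **Vaping group.** Do not exclude on cotinine, since a teen vaping on 10 of 30 days may be between uses.
3. **9.4.2.** Add a sensitivity analysis of cotinine-positive vapers against cotinine-negative controls. Note that it selects recent users and, because vaping continues as usual before the scan, may mix acute with chronic effects.
4. **Reconcile** the synopsis, which describes controls as having no vaping or smoking history, with 5.1, which allows up to five lifetime uses.

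**Cost.** Protocol wording and one extra analysis; no new sample or visit, apart from the occasional repeat test. A few controls will be lost, some through passive exposure, and replacements must be found who match on age, sex, race/ethnicity and SES. The rule will not detect all intermittent use or verify the lifetime limit, and the report should say so.

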5.2 Exclusion Criteria

An individual who meets any of the following criteria will be excluded from participation in this study based on self and or parent-report unless otherwise noted:

Vaping or Non-Vaping Group:

1. Chronic medical conditions associated with cerebral blood flow abnormalities per PI/MAI determination after review of the medical history.
2. Neurological conditions that may interfere with MRI data quality per PI/MAI determination after review of the medical history.

Abbreviated Title: Mindfulness and Teen Vaping

Version Date: 07/21/2025

NIH IRB#: IRB001855

3. Neurodevelopmental disorders that are likely to significantly affect data in the judgment of the MAI/PI
4. Non-penetrating traumatic brain injury with loss of consciousness > 30 minutes or significant sequelae persisting longer than 2 weeks or any penetrating traumatic brain injury.
5. Changing dose of psychotropic medication in past 3 months
6. Current regular meditation or yoga practice averaging >10 min/day for >2 days per week
7. Pregnancy, self-report upon protocol entry, but by urine test prior to MRI scan.

5.3 Inclusion of Vulnerable Participants

We will include children because this study focuses on effects of vaping unique to adolescents.

Non-English speakers are excluded because the questionnaires in this study are not all validated in languages other than English. We do not have the resources to translate the consent and questionnaires.

5.4 Participation of NIH Staff or family members of study team members

NIH staff and family members of study team members may be enrolled in this study. Neither participation nor refusal to participate as a subject in the research will have an effect, either beneficial or adverse, on the participant's employment or position at NIH.

Every effort will be made to protect participant information, but such information may be available in medical records and may be available to authorized users outside of the study team in both an identifiable and unidentifiable manner.

The *NIH Frequently Asked Questions (FAQs) for Staff Who are Considering Participation in NIH Research and Leave Policy for NIH Employees Participating in NIH Medical Research Studies (NIH Policy Manual 2300-630-3)* will be provided to subjects for them to review. Please see section **Error! Reference source not found.** for consent of NIH Staff.

5.5 Error! Reference source not found.Inclusion of Pregnant Women, fetuses or neonates

Pregnant women may not participate in this study.

5.6 Lifestyle Considerations

Participants will be instructed to abstain from cannabis, alcohol, and other street drugs for 24 hours and limit caffeine for 12 hours, prior to scan visits, but will be allowed to vape as usual. Abstinence will be verified on scan days via self-report, and UDT, with participants rescheduled if they test positive for THC or other drugs on UDT and fail a clinical assessment for intoxication. Participants in the vaping group will need to agree to participate in the MBSR training. One parent/guardian must be present for the consent process for participants under 18 y/o, and they will have the option to remain at NIDA while their minor is participating.

